7 EFFICACY ASSESSMENTS

The efficacy variables which will be assessed in this study are as follows:

- Mean absolute change in haemoglobin level (g/dl) in subjects before and after 6-months of treatment with EPIAO/EPREX
- Mean absolute change in weekly epoetin dosage per kg body weight (IU/kg/week) before and after 6-month treatment with EPIAO/EPREX.
- Proportion of subjects with any haemoglobin measurement outside the target range during the double-blind treatment period
- Incidence of blood transfusions

The haemoglobin assessment will be performed at all the scheduled visits and the epoetin dosage required for each subject will be calculated by the investigator and the same will be documented in the Electronic Case Report Form (eCRF).

8 SAFETY ASSESSMENTS

8.1 Adverse Events

All clinical adverse events occurring after the subject signs the ICF and up to 4 weeks after the last dose of study medication, whether observed by the investigator or reported by the subject, will be recorded on the Adverse Event CRF page. All serious adverse events (SAEs) are to be reported according to the procedures in Section 8.3 SAE Reporting-Procedure for Investigators. In addition, any untoward event that may occur subsequent to the reporting period that the Investigator assesses as related (definitely, possibly or probably) to study drug should also be reported and managed as an AE. Pre-planned procedure or hospitalization for pre-existing conditions which do not worsen in severity should not be reported as SAEs (see Section 8.1.1 for Definitions).

At each visit, the investigator will determine whether any adverse events have occurred by evaluating the subject. Adverse events may be directly observed, reported spontaneously by the subject or by questioning the subject at each study visit. Subjects should be questioned in a general way, without asking about the occurrence of any specific symptoms. All laboratory values must be appraised by the Investigator as to clinical significance. All post-baseline abnormal laboratory values considered clinically significant by the Investigator must be recorded in the adverse event page of the CRF.

Investigator should follow subjects with adverse events until the event has resolved or the condition has stabilized. In case of unresolved adverse events including significant abnormal laboratory values at the end of study assessment, these events will be followed up until resolution or until they become clinically not relevant.

8.1.1 Definitions

8.1.1.1 Adverse Event

Any untoward medical occurrence in a subject or clinical investigation subject administered a pharmaceutical product and which does not necessarily have to have a causal relationship with this treatment.

An AE is therefore any unfavorable and unintended sign (an abnormal ophthalmic finding, for example), symptom (including physical, psychological or behavioral effect), or disease temporally associated with the use of a medicinal (investigational or marketed) product, experienced by a patient or subject during their participation in an investigational study, in conjunction with the use of the drug or biologic, whether or not considered product-related.

This includes any untoward signs, symptoms, illness or clinically significant laboratory test abnormality that has appeared or worsened during the course of the clinical trial, experienced by the subject from the time of signing the informed consent until completion of the study. Throughout the subject's participation in the study, any new clinically significant

findings/abnormalities that meet the definition of an adverse event must be recorded and documented as an adverse event.

8.1.1.2 Serious Adverse Event

During clinical investigations, AEs may occur which, if suspected to be drug-related (adverse drug reactions), might be significant enough to lead to important changes in the way the medicinal product is used or developed (e.g., change in dose, population, needed monitoring, consent forms). This is particularly true for reactions that, in their most severe forms, threaten life or function.

Any untoward medical occurrence that at any dose:

- Results in death,
- Is life-threatening,
- Requires inpatient hospitalization or prolongation of existing hospitalization,
- Results in persistent or significant disability/incapacity,
- Is a congenital anomaly/birth defect, or
- Is an important medical event.

Note: The term “life-threatening” in the definition of “serious” refers to an event in which the subject was at risk of death at the time of the event; it does not refer to an event which hypothetically might have caused death if it were more severe.

Medical and scientific judgment should be exercised in deciding whether expedited reporting is appropriate in other situations, such as important medical events that may not be immediately life-threatening or result in death or hospitalization but may jeopardize the subject or may require intervention to prevent one of the other outcomes listed in the definition above. Examples include allergic bronchospasm, convulsions, and blood dyscrasias or development of drug dependency or drug abuse.

Note:

- A procedure is not an AE or SAE, but the reason for the procedure may be an AE.
- Pre-planned surgeries or hospitalizations for pre-existing conditions which do not worsen in severity are not SAEs.

Adverse Event Reporting Period

The study period during which adverse events must be reported is defined as the period from the initiation of any study procedures (after signing of ICF) up to 4 weeks after the last dose of study medication.

Medical History Condition

A medical history condition is any clinically significant medical/surgical condition already present at the time of screening *after informed consent*.

Pre-treatment Adverse Events

After informed consent during screening any clinically significant abnormality which meets the definition of AE should be recorded as a pre-treatment AE prior to the use of the product (Day 1) and should be recorded accordingly. Any new clinically significant event or worsening of existing medical history condition, which meets the definition of AE prior to the application of IP will also be considered as pre-treatment adverse event.

Post-treatment Adverse Events

All AEs recorded after the first dose of IP (Day 91) till the end of treatment will be considered as post-treatment AEs. Disease signs, symptoms and/or laboratory abnormalities already existing prior to the use of the product will not be considered as adverse experiences after treatment (post-treatment AEs) unless they reoccur after the subject/patient has recovered from the pre-treatment condition or they represent an exacerbation in intensity or frequency or the character of the condition worsens during the study period.

General Physical Examination Findings

At screening, any clinically significant abnormality should be recorded as a pre-existing condition. At the end of the study, any new clinically significant findings/abnormalities that meet the definition of an adverse event must also be recorded and documented as an adverse event.

Post-study Adverse Event

At the last scheduled visit, the investigator should instruct each subject to report any subsequent event(s) that occur within 14 days after discontinuation of treatment. The investigator should notify the sponsor of any death or adverse event occurring at any time after a subject has discontinued or terminated study participation that may reasonably be related to this study.

Abnormal Laboratory Values

A clinically significant laboratory abnormality should be documented as an adverse event if any one of the following conditions is met:

- The laboratory abnormality is not otherwise refuted by a repeat test to confirm the abnormality
- The abnormality suggests a disease and/or organ toxicity, then the underlying condition should be captured as an AE.
- The abnormality is of a degree that requires active management; e.g. change of dose, discontinuation of the drug, more frequent follow-up assessments, further diagnostic investigation, etc.

Lab abnormalities found during the screening tests will not be considered as adverse event.

Hospitalization, Prolonged Hospitalization or Surgery

Any adverse event that results in hospitalization or prolonged hospitalization should be documented and reported as a serious adverse event. Any condition responsible for surgery should be documented as an adverse event if the condition meets the criteria for an adverse event.

Neither the condition, hospitalization, prolonged hospitalization, nor surgery are reported as an adverse event in the following circumstances:

- Hospitalization or prolonged hospitalization for diagnostic or elective surgical procedures for a pre-existing condition. Surgery should not be reported as an outcome of an adverse event if the purpose of the surgery was elective or diagnostic and the outcome was uneventful.
- Hospitalization or prolonged hospitalization required to allow efficacy measurement for the study.
- Hospitalization or prolonged hospitalization for therapy of the target disease of the study, unless it is a worsening or increase in frequency of hospital admissions as judged by the clinical Investigator.

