5 TREATMENTS ADMINISTERED

5.1 Investigational Product(s)

The Investigator must ensure that the investigational product (IP) will be used only in accordance with the protocol. The drug will be manufactured complying with all required regulations. Sufficient quantities of the drug will be supplied to the clinical study facility by the sponsor. Batch

numbers and expiration dates will be filed in the study documents when available. See the table below for ingredient list of each product.

Table 1: Investigational Product Details

	Treatment	Comparator
Active Ingredient	Recombinant human erythropoietin	Recombinant human erythropoietin
Brand name	EPIAO	EPREX
Dosage form	Pre-filled syringe	Pre-filled syringe
Strength	2000 IU, 4000 IU	2000 IU, 4000 IU
Frequency	1-3 times per week	1-3 times per week
Route of administration	Intravenous	Intravenous
Manufactured by	Shenyang Sunshine Pharmaceutical Co., Limited	Janssen Pharmaceuticals, Inc.

For the purpose of this trial, study medication / study drug / study treatment / investigational product / IP refer to EPIAO of Shenyang Sunshine Pharmaceutical Co., Limited and EPREX of Janssen Pharmaceuticals, Inc.

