- Perform a standard general physical examination
- Vital signs including blood pressure, heart rate, respiratory rate, temperature
- Laboratory investigations (haematology, serum chemistry, urinalysis*, serology, fecal occult blood test (as per PI discretion), intact parathyroid hormone and iron study, reticulocyte count) (refer Table in Appendix I)
- BUN (pre and post hemodialysis)
- Immunogenicity testing for anti-EPO antibody
- Chest X ray^{\$}, ECG
- Adequacy of dialysis measurement by Kt/V formula

(K= dialyzer clearance; t= time; V= volume of body water)

The Kt/V calculator is a tool used by nephrologists to determine the adequacy of dialysis treatment. The DaVita Kt/V Calculator uses the Daugirdas II equation for Single Pool (spKt/V), the Leypoldt equation for Equilibrated Double Pool (eKt/V) and the Leypoldt equation for Standard (stdKt/V) calculations.

Calculate a Kt/V

Treatment time (min)	
# Treatments/week	
Blood Urea Nitrogen (mg/dL or mmol/L)	Pre-dialysis  Post-dialysis 
Weight (lbs or kgs)	Pre-dialysis  Post-dialysis 

Reset **Calculate**

- Serum Pregnancy Test (only for female subjects with child bearing potential)

*= Urinalysis test will be considered as optional for CKD patients as CKD patients may not be able to provide sufficient urine volume for urinalysis test due to low urine output. \$= Chest X ray performed within one year prior to screening of the subject is acceptable.

6.2 Titration period / Visit 1 – 7 (Week 1/Day 1 Week 2/Day 14, week 4/Day 28, week 6/Day 42, week 8/Day 56, week 10/Day 70 and week 12/Day 84) with window period of \pm 2 days

All the eligible subjects will enter the titration period (starting from week 1). The subjects will undergo haemodialysis one to three times a week. .

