EPREX will be administered one to three times weekly as per last dose which subject received previously before screening in order to maintain the haemoglobin within the target range of 10 to 12.5 g/dl with intra individual change in the Hb of ≤ 1.2 g/dl over 4-week period before randomization i.e. during Week 8/Day 56 (V5), Week 10/Day 70 (V6) and Week 12/Day 84 (V7). The subject with target range Hb and intra individual change of ≤ 1.2 g/dl during V5, V6 and V7 will be considered as stable on Hb and will be scheduled in next week for randomization to appropriate arm after performing V8 procedure. The titration period of three months is considered based on the EMA guidelines [Guideline on non-clinical and clinical development of similar biological medicinal products containing recombinant erythropoietins (Revision)] which states that “Patients included in a maintenance phase study should be optimally titrated on the reference product (stable haemoglobin in the target range on stable epoetin dose and regimen without transfusions) for a suitable duration of time (usually at least 3 months)”.

If subject fails to achieve target range Hb and intra individual change of ≤ 1.2 g/dl at week 12 (V7), such subject will enter into extended titration period. The extension of titration period will be performed every two weeks [Extended Week 14/Extended Day 98 (EV8), Extended Week 16/Extended Day 112 (EV9), Extended Week 18/Extended Day 126 (EV10) and Extended Week 20/Extended Day 140 (EV11)] for a maximum of 8 weeks after Week 12/Day 84 (V7). The assessment which will be performed in the extended titration period every two weeks will be similar to visit 7 assessments (Week 12/Day 84).

If subject fails to achieve target range Hb and intra individual change of ≤ 1.2 g/dl at week 12 (V7), the next evaluation of the subject will be done at Extended Week 14/Extended Day 98 (EV8) followed by Extended Week 16/Extended Day 112 (EV9). The target Hb range and intra individual change in Hb will be compared over Week 12/Day 84 (V7), Extended Week 14/Extended Day 98 (EV8) and Extended Week 16/ Extended Day 112 (EV9). If the subject with target range Hb and intra individual change of ≤ 1.2 g/dl is achieved during Extended Week 16/ Extended Day 112 (EV9), subject will be scheduled in next week for randomization and will perform V8 procedure.

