If subject fails to achieve target range Hb and intra individual change of ≤ 1.2 g/dl at Extended Week 16/Extended Day 112 (EV9), such subject will continue the extension of titration period [Extended Week 18 (EV10/Extended Day 126) and Extended Week 20 (EV11/Extended Day 140)]. The extended titration period will be performed every two weeks. The assessment which will be performed in the extended titration period every two weeks will be similar to visit 7 assessments (Week 12/ Day 84). The target Hb range and intra individual change in Hb will be compared over Extended Week 16/Extended Day 112 (EV9), Extended Week 18/ Extended Day 126 (EV10) and Extended Week 20/ Extended Day 140 (EV11). If the subject with target range Hb and intra individual change of ≤ 1.2 g/dl is achieved during Extended Week 20/Extended Day 140 (EV11), subject will be scheduled in next week for randomization and will perform V8 procedure.

If the subject fails to achieve target range Hb and intra individual change of ≤ 1.2 g/dl at Extended Week 20/Extended Day 140 (EV11), such subject will be considered as screen failure.

The following assessments will be performed at week 2/Day 14, week 6/Day 42 and week 10/Day 70 at defined visit window;

- Demographic data (body weight: pre and post hemodialysis)

- Physical examination
- Vital signs
- Complete Blood Count (CBC)
- Adverse events
- Concomitant medication
- Dose adjustment if required as per section 5.1.7

The following assessments will be performed at the end of week 4/Day 28, week 8/ Day 56 and week 12/ Day 84;

- Demographic data (body weight: pre and post hemodialysis)
- Physical examination
- Vital signs
- Adverse events
- Concomitant medication
- Dose adjustment if required as per section 5.1.7
- Immunogenicity testing for anti-EPO antibody*
- Hematology
 - ✓ Haemoglobin
 - ✓ Haematocrit
 - ✓ Total WBC count
 - ✓ Differential WBC count
 - ✓ Platelet count
 - ✓ Red Blood Cell count
 - ✓ Reticulocyte count&
 - ✓ MCV
 - ✓ MCH
 - ✓ MCHC
 - ✓ Peripheral smear
 - ✓ Iron study#

* Only during week 8

Only during week 10

& Only during week 12/Day 84

The following assessments will be performed at the end of Extended Week 14/Extended Day 98 (EV8), Extended Week 16/ Extended Day 112 (EV9), Extended Week 18/Extended Day 126 (EV10) and Extended Week 20/Extended Day 140 (EV11) (as applicable for extended titration period) with window period of ± 2 days

- Demographic data (body weight: pre and post hemodialysis)
- Physical examination

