9.2.1 Missing data

Efficacy

No imputation will be done on missing efficacy data.

Safety

No imputation will be done on missing safety data, unless otherwise stated below

Dates

Dates of remote events (e.g. AEs or concomitant medication) may be partially incomplete, as the day and/or month may be unknown. AEs with incomplete start dates will be considered as

treatment emergent, only if they are definitely known to have started after randomization. For treatment, emergent AEs with incomplete start dates (unknown date and known month), the start date will be taken as the first of the corresponding month or date of randomization, whichever is later. Incomplete dates for concomitant medications will not be imputed.

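### The adverse-event periods use two different start days, so events from the common EPREX titration phase can be tabulated under the EPIAO arm

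*Protocol*

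**What the plan says.** Section 8.1.1.2 defines two periods.

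- **Pre-treatment.** After consent, a clinically significant abnormality found during screening "should be recorded as a pre-treatment AE prior to the use of the product (Day 1" is the first case. A second sentence adds any new or worsening event "which meets the definition of AE prior to the application of IP will also be considered as pre-treatment adverse event".
- **Post-treatment.** "All AEs recorded after the first dose of IP (Day 91) till the end of treatment will be considered as post-treatment AEs". A following clause leaves out conditions already present before the product was used, unless they recur after recovery or get worse.

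Section 5.1 fixes the vocabulary: the terms "investigational product / IP refer to EPIAO of Shenyang Sunshine Pharmaceutical Co., Limited and EPREX of Janssen Pharmaceuticals, Inc". Section 6.2 says "All the eligible subjects will enter the titration period (starting from week 1" and, of the drug given in that phase, "EPREX will be administered one to three times weekly as per last dose which subject received previously before screening". Visit 1 is Week 1/Day 1. Section 6.3 puts randomisation at Visit 8, Week 13/Day 91.

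On analysis, section 8.1 collects adverse events from consent onwards, and section 9.1 puts all randomised subjects in the safety cohort. Section 9.5.1 summarises all adverse events and gives the number and proportion of subjects affected by treatment group, with no condition on when the event began. Section 9.2.1 treats an event with an incomplete start date as treatment emergent "only if they are definitely known to have started after randomization".

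**The concern.** Two adjacent definitions describe the start of product use, one with Day 1 and one with Day 91. Between those days every subject is on the reference product, before any randomised difference exists. What happens to an event that starts in that interval depends on whether the reader follows the defined term IP or the printed day.

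The frequency of adverse events after EPIAO and after EPREX is a secondary objective (section 2.1.2), and drug-related events are a safety endpoint (section 3.1.3). If titration events enter the comparison, both arms carry the same kind of EPREX background. The arms then look more alike than the randomised treatments make them. An event that began on EPREX, even one judged drug-related, could be reported as an EPIAO event.

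The clause on pre-existing conditions inherits the problem. If product use starts on Day 1, an event that arose during titration and persists unchanged after the switch is not pre-existing. If it starts at the first randomised dose, it is.

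**Working it through.** **Step 1: the printed day.** Week 13 × 7 = Day 91, so Day 91 is the nominal day of Visit 8 (section 6.3). It is the day of the first randomised dose. It is not the first dose of IP as section 5.1 defines IP, because EPREX starts at Week 1/Day 1 (section 6.2).

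**Step 2: the possible readings.**

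| Reading | First dose of IP | Event starting on Days 1–90 |
|---|---|---|
| Defined term (5.1) governs | Day 1 | Post-treatment, under the arm assigned later |
| First randomised dose meant, titration EPREX not IP | Visit 8 | Pre-treatment, by the second pre-treatment sentence |

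The second reading is benign. It needs titration EPREX not to be IP, which section 5.1 contradicts, and it does not fit the printed Day 1.

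**Step 3: does the analysis section settle it?** Section 9.5.1 covers all adverse events by treatment group in randomised subjects, and titration events are collected. Nothing there removes them. Section 9.2.1 limits treatment-emergent status to events after randomisation, but only for incomplete start dates.

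**Step 4: size under the defined-term reading.**

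- Titration, Day 1 to Day 90: 90 days.
- Randomised treatment, Day 91 to Day 448 (Week 64 × 7): 448 − 91 + 1 = 358 days.
- Share of on-drug time: 90 / (90 + 358) = 90/448 = 20%. With the nominal 52 weeks (364 days) it is 90/454 = 19.8%.
- EPREX exposure carried into the planned EPIAO arm: 132 × 90 / 365.25 = 32.5 patient-years, if all 132 subjects have the nominal titration.
- Interim analysis at Visit 16 (Day 252), which section 9.6 says includes safety: 90/252 = 36%.

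**Step 5: direction of the effect.** Let a and b be the proportions with at least one event after the switch, and t the proportion with one during titration, the same in both arms and independent. The observed proportions are 1 − (1 − a)(1 − t) and 1 − (1 − b)(1 − t), so the difference shrinks by the factor 1 − t. The protocol gives no event rates. Assume a = 30%, b = 20%, and t = 15%, with half and double that value:

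| t | Arm 1 | Arm 2 | Difference | Ratio |
|---|---|---|---|---|
| 0 | 30% | 20% | 10 points | 1.50 |
| 7.5% | 35.25% | 26% | 9.25 points | 1.36 |
| 15% | 40.5% | 32% | 8.5 points | 1.27 |
| 30% | 51% | 44% | 7 points | 1.16 |

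The figures illustrate direction only. The attenuation holds for any t above zero.

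**The case against.** The strongest reply is that the intent is clear. The post-treatment sentence prints Day 91, Table 2 places the start of dosing with randomisation at the baseline visit, and the protocol separates titration (6.2) from the treatment period (6.4). The second pre-treatment sentence would then take in titration events, and section 9.2.1 points to the same start. Sections 9.5 and 9.5.1 never use the pre- and post-treatment labels, the analysis is descriptive, and a statistical analysis plan may define treatment-emergent events. Finally, 20% is exposure time, not events.

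Much of this stands. The first randomised dose is probably what was meant, and it rules out three stronger inferences that a reader might draw:

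- **That titration events necessarily belong to neither class.** This follows only if both printed days are taken literally and the second pre-treatment sentence is ignored.
- **That subjects with extended titration carry 28 or 56 days of pre-randomisation EPREX events past Day 91.** Section 6.2 does say that if stability "is achieved during Extended Week 20/Extended Day 140 (EV11), subject will be scheduled in next week for randomization", and counting elapsed days gives 119 − 91 = 28 after the earlier extension check and 147 − 91 = 56 after the last. But extension visits have their own Extended Day labels, while plain Days 98, 112 and 140 are treatment Visits 9, 11 and 12. Day 91 is the nominal label of Visit 8 for every subject, extended or not.
- **That section 9.2.1 adds a third anchor.** Randomisation is Visit 8, so it agrees with the printed Day 91.

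The intent does not remove the conflict. The benign reading contradicts the definition of IP in section 5.1 and the printed Day 1, and section 9.5.1 does not carry it through. That the labels are unused in 9.5.1 is part of the difficulty, because all events are then tabulated by arm. Nor is this a detail merely left to a later plan: the protocol states the rule, and states it inconsistently.

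**Conclusion.** The inconsistency is real and should be corrected. It makes the safety comparison ambiguous, but does not show that it will be biased. The harm arises only if the defined term IP is followed, or if section 9.5.1 is applied literally. About 20% of a completer's on-drug time would then be common EPREX exposure, the arms' adverse-event proportions would be drawn together, and EPREX-onset events could appear under EPIAO.

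The 20% assumes completion to Day 448 and no extension. A subject with full extension would have 146 titration days, so 146 / (146 + 358) = 29%. The protocol gives no extension rate, so that is not an arm-level figure. The co-primary efficacy analyses are not affected.

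**What to change.** - **8.1.1.2:** replace both day anchors with each subject's actual first randomised dose at Visit 8, and judge whether a condition is pre-existing or has worsened against that same time.
- **9.5.1:** state that the comparison between arms counts only adverse events that start or worsen from that dose.
- **Titration events on EPREX:** list them separately, so that they stay visible without entering the comparison.
- **9.2.1:** keep the rule for incomplete dates consistent with this anchor.

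The cost is protocol wording, matching text in the statistical analysis plan and one programming flag. The dates needed are already collected, and no treatment, visit or clinical management rule changes.

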3.1.5 Duration of Subject Participation

The duration of the subject participation will be of a maximum of 68 weeks, (77 weeks in case of extension of titration period) including 4 weeks of screening period, titration period of at least 3 months (maximum duration for 5 months), treatment duration of 26 weeks for efficacy and safety evaluation (weeks 13 through weeks 39) and treatment duration of 26 weeks for immunogenicity evaluation (weeks 40 through weeks 64). In substantiated cases a prolongation of the titration period is allowed up to maximum of 4 to 5 months on a case to case basis which will be considered as extended titration period. The assessment will be similar to the visit 7 (week 12/Day 84) if there is prolongation of the titration period.

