6.5 End of Treatment / Study

Visit 23: End of study visit Week 64/ Day 448

- Demographic data (body weight: pre and post hemodialysis)
- Vital signs
- Physical examination
- Adverse events
- Concomitant medication
- Laboratory investigations (haematology, serum chemistry, urinalysis* and iron study and reticulocyte count) (refer Table in Appendix I)
- Chest X ray, ECG
- Serum Pregnancy Test (for all females of childbearing potential)
- Immunogenicity testing for anti-EPO antibody
- BUN (pre-and post Dialysis)
- Adequacy of dialysis measurement by Kt/V formula

*= Urinalysis test will be considered as optional for CKD patients as CKD patients may not be able to provide sufficient urine volume for urinalysis test due to low urine output.

Table 2: Study Visit Plan

S No .	Procedures	Screen ing	Titration period							Extend ed Titrati on period	Baseli ne*	Treatment Period												End of Study		
		V 0 (Day - 31 to Day 0)	V 1 (Wk 1/ Day 1)	V 2 (Wk 2/D ay 14)	V 3 (Wk 4/Da y 28)	V 4 (Wk 6/D ay4 2)	V 5 (Wk 8/Day 56)	V 6 (Wk 10/Da y 70)	V 7 (Wk 12/D ay 84)			V 8 (Day 91/ Week 13)	V 9 (Wk 14/ Day 98)	V 10 (Wk 15/ Day 105)	V 11 (Wk 16/ Day 112)	V 12 (Wk 20/ Day 140)	V 13 (Wk 24/ Day 168)	V 14 (Wk 28/ Day 196)	V 15 (Wk 32/ Day 224)	V 16 (Wk 36/ Day 252)	V 17 (Wk 40/ Day 280)	V 18 (Wk 44/ Day 308)	V 19 (Wk 48/ Day 336)	V 20 (Wk 52/ Day 364)	V 21 (Wk 56/D ay 392)	V 22 (Wk 60/ Day 420)
1	Informed Consent	X																								
2	Demographic Data ¹	X		X	X	X	X	X	X															X	X	
3	Medical History	X																								
4	Menstrual and Reproductive History	X																								
5	Physical/Clinical Examination ²	X		X	X	X	X	X	X															X	X	
6	Vital signs ³	X		X	X	X	X	X	X															X	X	
7	Inclusion & Exclusion Criteria	X																								
8	Eligibility Criteria											X														
9	Concomitant Medication ⁴	X		X	X	X	X	X	X															X	X	
10	Peripheral smear	X			X		X		X																	X
11	Complete Blood Count	X		X	X	X	X	X	X															X	X	
12	Reticulocyte Count	X							X	X																X
13	Renal Function (BUN)	X										X													X	X
14	Iron study	X						X				X												X		X
15	CRP																									X
16	Liver Function Test ⁵																									X
17	Serum Chemistry	X																								X
18	HbA1C	X																								X
19	Urinalysis ⁶	X																								X
20	Serology	X																								X

21	Fecal occult¹⁰ blood test & intact parathyroid hormone	X																						

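### Adverse events must be recorded for 4 weeks after the last dose, but subjects are asked to report only the first 14 days, so days 15–28 are not solicited

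*Protocol*

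**What the plan says.** The Protocol gives four different end points for AEs.

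- **Section 8.1** covers "All clinical adverse events occurring after the subject signs the ICF and up to 4 weeks after the last dose of study medication", whether the investigator observes them or the subject reports them.
- **Section 8.1.1.2, Adverse Event Reporting Period**, repeats that limit: "up to 4 weeks after the last dose of study medication".
- **Section 8.1.1.2, Post-study Adverse Event**, has the investigator instruct each subject at the last scheduled visit to "report any subsequent event(s) that occur within 14 days after discontinuation of treatment".
- **Section 8.1.1.2, Post-treatment Adverse Events**: "All AEs recorded after the first dose of IP (Day 91) till the end of treatment will be considered as post-treatment AEs".
- **Section 8.1.1.1**, in defining an AE, uses the period "from the time of signing the informed consent until completion of the study".

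The schedule ends with "Visit 23: End of study visit Week 64/ Day 448" (section 6.5). Section 3.1.5 sets participation at a "maximum of 68 weeks, (77 weeks in case of extension of titration period) including 4 weeks of screening period". Neither section mentions a visit or telephone contact afterwards.

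Two provisions reach further. Section 8.1 also requires events after the reporting period to be reported if the investigator assesses them as related. The sentence following the 14-day instruction requires the sponsor to be told of a death or AE at any later time that may reasonably be related to the study.

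**The concern.** The length of the safety tail is fixed by what the site must record. What the site gets to hear is fixed by what subjects are asked. Here the two differ by a factor of two. After Visit 23 the instruction to the subject is the only solicitation that the Protocol describes, and it stops halfway through the required window.

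AE frequency is a secondary objective (section 2.1.2), and the incidence and nature of AEs is a safety endpoint regardless of causality (section 3.1.3). Section 8.9 names hypertension and thromboembolic events as of specific interest. Under-reporting in the tail would lower AE counts and weaken the safety comparison. A statistical analysis plan could define a table class, but it could not recover events that nobody asked about.

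**Working it through.** No sample size, power or error rate is involved. The check compares time windows, counted in days after the last dose. It assumes that discontinuation of treatment and last dose are the same day.

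| Place in Protocol | Purpose | End point |
|---|---|---|
| 8.1 | Recording of AEs | Day 28 |
| 8.1.1.2, Reporting Period | Reporting of AEs | Day 28 |
| 8.1.1.2, Post-study | What subjects are told | Day 14 |
| 8.1.1.2, Post-treatment | Class of the AE | Day 0 |
| 8.1.1.1 | Definition of an AE | Completion of the study |

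**Unsolicited part.** 28 − 14 = 14 days (days 15–28), and 14 / 28 = 50% of the tail.

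**Does any visit cover the tail?** With the last dose at about Day 448, the tail ends at 448 + 28 = Day 476, and 476 / 7 = Week 68 of the study calendar. Adding 4 weeks of screening gives 72 weeks. The stated maximum without extension is 4 + 64 = 68 weeks, so the tail lies 72 − 68 = 4 weeks beyond scheduled participation. If dosing were once weekly and the last dose fell up to 7 days before Visit 23, the tail remaining after that visit would be 21 to 28 days and the instructed part 7 to 14 days. The difference is 14 days either way.

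**Share of the whole post-randomisation period.** 52 × 7 + 28 = 392 days, and 14 / 392 = 3.6%.

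**What happens to an AE, by start day:**

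- Days 1–14: must be recorded and is solicited.
- Days 15–28: must be recorded if the site learns of it, but is not solicited.
- After day 28: reported only if judged related.

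**Class.** The post-treatment class closes at end of treatment, so it covers 0 of the 28 days. The pre-treatment class concerns events before the product is used. An AE starting on any day of the tail therefore belongs to neither.

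**Start of the class.** It opens at the first dose of IP, with Day 91 in brackets. Section 5.1 counts EPREX as IP and EPREX is given during titration, so the words do not by themselves single out the first randomised dose.

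**The case against.** The strongest reply is that the 14-day sentence governs only what subjects are told. It does not shorten collection: any AE the site learns of within 4 weeks must still be recorded. That stands, and it limits the harm to events that go unheard. Several stronger readings are tempting, and the text does not support them.

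- **Late events are lost.** Too absolute. Days 1–14 are solicited, and the two provisions without a time limit keep events judged related, and deaths that may be related. Thrombosis is a listed expected event (section 8.2), so once known it is a likely candidate for a related assessment. These routes still depend on the site hearing of the event and on a causality judgement.
- **After Visit 23 the site can learn of events only through the subject.** Not stated. These patients attend for haemodialysis one to three times a week (sections 5.1.8 and 6.4). The Protocol does not say whether dialysis at the site continues after Week 64, and does not use it for follow-up.
- **Tail events are dropped from the safety tables.** Sections 9.5 and 9.5.1 summarise all AEs and never use the post-treatment class. The only emergence rule in section 9 (9.2.1, for incomplete start dates) relies on a start after randomisation, with no upper limit. The class is undefined for the tail, but no exclusion follows from that.
- **Titration events in extended-titration subjects count as post-treatment from calendar Day 91.** Such subjects are randomised in the week after Day 112 or Day 140, so about Day 119 or Day 147. But Day 91 can be read as the nominal label of Visit 8, whose procedures they perform when they are randomised.

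For subjects who stop early, section 4.2.2 requires asking about AEs, completing the last scheduled assessments and following AEs up. This covers events known at the time of stopping; it sets no contact at 4 weeks.

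**Conclusion.** The Protocol contradicts itself on the AE follow-up window and should be corrected. The supported conclusion is limited: AEs starting on days 15–28 after the last dose, chiefly those not judged related, are required but not solicited and may be under-collected. AEs starting at any time after end of treatment have no defined class, and the AE definition carries a further end point.

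The 50% is a share of calendar days, not of events. The Protocol gives no event rate for the tail, so the number of AEs missed cannot be estimated. The gap applies to both arms alike and is probably similar in effect. This rests on two assumptions: that discontinuation means the last dose, and that no post-study contact is arranged outside the Protocol. It is a clear and correctable inconsistency, not a threat to the equivalence conclusions.

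**What to change.** Reconcile sections 8.1, 8.1.1.1 and 8.1.1.2 to the one end point that is already stated twice, 4 weeks after the last dose:

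1. In Post-study Adverse Event, change the instruction to subjects from 14 days to 4 weeks.
2. Define post-treatment AEs as those starting from the first randomised dose up to 4 weeks after the last dose, with Day 91 kept only as the nominal day.
3. In section 8.1.1.1, replace completion of the study with the same end point.

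These are wording changes, and the cost is a few more AEs to record. A short contact at the end of the 4 weeks would make the solicitation active, at the price of one extra contact per subject; it is a useful addition but not needed to remove the contradiction.
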